9.2.2 Demographic Information and Clinical History

Background and demographic data of all subjects included in this clinical study will be assessed by group. Descriptive statistics (mean, standard deviation, median, minimum, and maximum) will be provided for continuous variables (age, height, weight, BMI, etc.) and the frequency and percentage will be provided for categorical variables (gender, medical history, etc.).

To compare the difference between the groups, the two-sample t-test or the Wilcoxon rank sum test will be carried out for continuous variables, and Chi-square test or Fisher's exact test will be carried out for categorical variables.

9.2.3 Efficacy Endpoints

9.2.3.1 Primary Efficacy Assessment

Proportions of subjects with symptoms relief at Week 4

The proportions of subjects with symptoms relief by Week 4 and their 95% confidence intervals will be provided by group.

The proportions of subjects with symptoms relief by Week 4 will be calculated as the cumulative symptoms relief by using the results at the time of final observation including the Withdrawal visit. To compare the control group and study group, the lower bound of the 2-sided 95% confidence intervals will be obtained by using Chi Square test or Fisher's Exact test method. If this lower bound is greater than the non-inferiority margin of -0.1, the study group will be judged to be non-inferior to the control group.

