 - c. Cholinergic drugs, anticholinergic drugs, and antispasmodics
 - d. Psychotropic drugs: Antipsychotics drugs, antidepressants, antimanic drugs, antianxiety drugs, and hallucinogenic agents, etc.
 - e. Steroids (allowed if used in a local application)
 - f. Antithrombotic drugs (antiplatelet drugs and anticoagulants)
 - g. Mucoprotective drugs
- 10) Those who need to take any prohibited concomitant medication during clinical study. (Only Antacid and Prokinetic permitted as rescue drug. The use of Antacid and Prokinetic during the study period will be recorded as subject's prior/concomitant medication)
- 11) Those who took the other investigational product within 4 weeks prior to administration of investigational product.
(But it is possible to enroll in the study [i.e., observational study, retrospective study] that doesn't affect this study's efficacy and safety as determined by the investigator.)

[Laboratory tests]

- 12) At screening, those who had
 - a. serum alanine aminotransferase (ALT), aspartate aminotransferase (AST), or total bilirubin levels $\geq 2 \times$ upper limit of normal
 - b. serum creatinine or BUN $\geq 2 \times$ upper limit of normal

[Others]

- 13) Pregnant or breast-feeding women
- 14) Those who do not consent to use appropriate contraceptive methods during the study.
Appropriate contraceptive methods for patients or their partners:
- For Male subject: to use barrier method such as male condom and surgical sterilization such as vasectomy;
- For Female subject: to use 1) hormonal contraceptive such as Intrauterine system : intrauterine hormone-containing system, implant, injection, contraceptive pills, or 2) non hormonal contraceptive such as Intrauterine system : copper loop,

barrier method : female condom, diaphragm or cervical cap, or surgical sterilization : tubectomy.

15) In the opinion of the investigator, those who were unsuitable for any reason.

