3.4 Criteria for Withdrawal

The subjects are allowed to spontaneously discontinue participation in this study at any time. The investigator may discontinue participation of a subject in this study at any time as per the subject's decision. However, a subject who are terminated early for showing a sufficient level of efficacy of the investigational product will not be considered as a withdrawal. If a subject is withdrawn from the study, the study results obtained from the discontinued/withdrawal case until the time point of discontinuation/withdrawal may be reviewed for evaluable items at the final evaluation.

In following cases, the investigator may withdraw the subject from the study.

- 1) Violation of inclusion/exclusion criteria is identified during the study.
- 2) Subjects are considered difficult to continue with the study due to adverse events as per the investigator's decision.
- 3) Subjects have received or are deemed to require medications or treatments that may affect the study results during treatment period or follow-up period.
- 4) Voluntary consent withdrawal by the subject or subject's legally acceptable representatives.
- 5) Subjects cannot not cooperate with the investigator.
- 6) Lost to follow-up.
- 7) The investigator decides to withdraw subjects.
- 8) Subject is pregnant during the study

If a subject determines to discontinue his/her participation and withdrawn from the study prior to completion, procedures scheduled for the Withdrawal visit should be performed. The procedure for the Withdrawal visit will be conducted within 2 weeks after the withdrawal decision is made. At the Withdrawal visit, the unused IPs or empty packaging will be returned, and the subject diary will be collected.

If the patient refused to visit, the vital sign, physical examination and lab test can be exclude. However, assessment of Gastroesophageal Reflux Disease Questionnaire (GERD-Q) and quality of life questionnaire (GERD-HRQL) must be performed at least by telephone call by the investigator, and all document should be written on the EMR by the investigator.s. To prevent any missing AEs that the investigator is not aware of, all kinds of methods must be employed to directly contact the subjects who refuse to visit such as phone call, letter, or personal visit. Any withdrawn subject cannot participate in the same study again.

4 Description of Study Design

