- 12) If a subject decides to discontinue participation or is withdrawn from the study before completion, the Withdrawal visit procedures will take place within 2 weeks from the withdrawal decision. At the Withdrawal visit, the unused IPs or empty packaging will be returned, and the subject diary will be collected. However, assessment of Gastroesophageal Reflux Disease Questionnaire (GERD-Q)^{*)} and quality of life questionnaire (GERD-HRQL)^{*)} must be performed. If the patient refused to visit, above two Questionnaires can be done by telephone call and the document should be written on the EMR by the investigator.
- 13) Subjects who have not been healed after the Treatment 1 of investigational product administration will have an additional 4-weeks of treatment period (Treatment 2) with the same mode of administration.

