9.1 Analysis Sets

Per Protocol Set (PPS)

The PPS will include the subjects in the FAS who complete the study without any major protocol deviation. Major protocol deviations include 'violation of the inclusion and exclusion criteria', 'administration of prohibited concomitant medications during the study', etc. (see Section "13.5 Protocol Deviations"), and the subjects with other major deviations will be determined at the case report adjudication meeting prior to disclosure of randomization codes.

Full Analysis Set (FAS)

The FAS will include the subjects who receive the IP at least once after randomization and who have at least one efficacy assessment result. The subjects who violate the inclusion/exclusion criteria will be excluded from the FAS.

For the efficacy analysis, they will be included in the randomized treatment group regardless of the actual IP taken.

Safety Set

The safety set will include all the subjects who receive the IP at least once after randomization. The subjects who are enrolled in the study but withdrawn from the study before IP administration will be excluded from the safety set. For the safety analysis, the subjects will be analyzed according to the treatment they actually received.

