9.2 Statistical Analysis Method

9.2.1 General Principles of Result Analysis

The efficacy analysis will be conducted primarily on the PPS and FAS, and the PPS will be the primary analysis set.

In principle, all statistical analyses will use SAS® version 9.4 or higher and be performed with a two-sided test at a significance level of 5%, unless otherwise specified.

Descriptive statistics (mean, standard deviation, median, minimum, and maximum) will be calculated and provided for continuous variables, and the frequency and percentage will be provided for categorical variables.

The last observation carried forward (LOCF) method will be applied for correction of missing data of continuous endpoints among efficacy endpoints, and if the LOCF method cannot be applied, the raw data will be analyzed without correcting the missing data. However, the quality-of-life score (GERD-HRQL) will be analyzed using the raw data without applying the LOCF. For survival analysis, censoring will be utilized. When applying the LOCF, if the value immediately before the missing value is the baseline value, it will not be replaced.

The missing values of efficacy endpoints will be handled for both analyses on the FAS and PPS, and the safety endpoints will be analyzed with the raw data without replacing the missing values.

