13.5 Protocol Deviation

If any protocol deviation becomes known during the study, the investigator should notify the deviation to the sponsor as soon as possible and decide whether to continue participation of the subject in the study. The followings are regarded as major protocol deviations:

- 1) Violation of inclusion and exclusion criteria
- 2) Administration of prohibited concomitant medications/therapies that may affect the study results
- 3) Treatment compliance of <80% or >120%
(Treatment compliance refers to the mean treatment compliance throughout the study treatment period for Fexuprazan 40 mg).
- 4) Other deviation considered as a major protocol deviation

For other minor deviations, the degree and reason of deviation or delay will be described accurately, and consideration on whether the study has been affected will be made at the time of result analysis.

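### The FAS can score a failure of the assigned drug as relieved when the final GERD-Q is answered on a doctor-given acid suppressant, and the primary PPS drops the same subject

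*Combined protocol and SAP*

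**What the plan says.** - **Endpoint rule (9.2.3.1).** The primary proportion is the "cumulative symptoms relief by using the results at the time of final observation including the Withdrawal visit".
- **Withdrawal (3.4).** One reason for which the investigator may withdraw a subject is: "Subjects have received or are deemed to require medications or treatments that may affect the study results". The GERD-Q is still required at withdrawal, by telephone if the subject will not attend.
- **Timing (8.2, note 12).** "the Withdrawal visit procedures will take place within 2 weeks from the withdrawal decision".
- **Care after early termination (13.6).** It follows usual GERD management. Section 1.2 says PPIs remain first-line in Indonesia.
- **Questionnaire (Attachment 2).** The GERD-Q covers the last 7 days. Item 6 asks about extra medicine other than what the doctor gave.
- **Analysis sets (9.1, 9.2.1, 13.5).** "The PPS will include the subjects in the FAS who complete the study without any major protocol deviation", and a listed major deviation is "Administration of prohibited concomitant medications/therapies that may affect the study results". For efficacy, "the PPS will be the primary analysis set", with the FAS alongside.
- **Missing data (9.2.1).** LOCF covers continuous endpoints only.

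No section requires the GERD-Q before a new acid suppressant starts, sets aside a score obtained on one, or counts such a subject as not relieved.

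**The concern.** A subject whose reflux is not controlled on the assigned drug, and who is moved to another acid suppressant, has failed that drug. Read together, these rules let both analysis sets miss the failure. The FAS may credit the assigned drug with relief produced by the replacement, and the PPS removes the subject. Both raise the apparent relief rate, and they raise it more in the arm with more failures. In a non-inferiority comparison that is the direction that helps the claim, so agreement between FAS and PPS would not be the reassurance it usually is. The trial is open-label, so the decision to switch can also differ by arm. The concern is limited to the prohibited acid suppressants of 7.3.2. It does not extend to antacid or prokinetic rescue, which is permitted.

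**Working it through.** **1. The plan's own figure.** Inputs from 9.4.2: control 0.885, fexuprazan 0.940, margin 0.10, one-sided 0.025, 1:1 allocation. With pooled variance, power = Φ[((0.940 − 0.885 + 0.10) − 1.96·s0)/s1]. At n = 53, s0 = √(2 × 0.9125 × 0.0875/53) = 0.0549 and s1 = √((0.885 × 0.115 + 0.940 × 0.060)/53) = 0.0546. Power is 0.80729, as stated. Then 53/0.8 rounds up to 67 per arm, 134 in total. The sample size reproduces.

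**2. GERD-Q of a symptom-free subject.** Items 3 and 4 are reverse-scored, so no epigastric pain and no nausea give 3 + 3. The total is 0 + 0 + 3 + 3 + 0 + item 6.
- Doctor-given drug: 6, relieved.
- Own extra medicine on 1 day: 7, relieved.
- Own extra medicine on 2-3 days: 8; on 4-7 days: 9; both not relieved.

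Item 6 therefore catches most self-medication but not a prescription.

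**3. Timing.** If the replacement starts s days after the decision and the GERD-Q is on day v ≤ 14, then min(7, v − s) recall days fall on it. With v = 14, any start in the first 7 days puts the whole recall on the new drug. The documents do not state s.

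**4. False-claim rate.** Truth is set at the margin: control 0.885, fexuprazan 0.785. Let f be the assumed share of failures who switch, the same in both arms, and g the share of switchers who score below 8. For each arm with relief rate p:
- PPS (53 per arm): p/(1 − f(1 − p)).
- FAS (67 per arm): p + g·f·(1 − p).

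The probability that the lower 95% Wald limit exceeds −0.1 comes from exact binomial enumeration. Wald is my assumption, because the plan names chi-square or Fisher tests but no interval formula.

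| f | PPS | FAS, g = 0.5 | FAS, g = 1 |
|---|---|---|---|
| 0 | 3.1% | 3.0% | 3.0% |
| 5% | 3.5% | 3.2% | 3.6% |
| 10% | 3.9% | 3.6% | 4.3% |
| 25% (illustration) | 5.8% | 4.7% | 7.8% |
| 50% (illustration) | 13.8% | 7.8% | 23.4% |

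At f = 10% the expected switchers per 67 are 67 × 0.215 × 0.10 = 1.4 on fexuprazan and 67 × 0.115 × 0.10 = 0.8 on control. If instead 5% of all subjects switch in each arm, the rates are 2.8% (PPS) and at most 3.6% (FAS).

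**5. Sensitivity to one subject.** With 59/67 relieved on drug in each arm, the Wald lower limit is −0.110 and the claim fails. If one fexuprazan failure is scored relieved (60/67), it is −0.092. If that subject is dropped (59/66), it is −0.094. Both pass. This is an illustration, not a forecast.

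**The case against.** **The route needs a chain of events.** The subject must fail before Day 28, be withdrawn or switched at the investigator's discretion, start a prescribed acid suppressant before the final GERD-Q, and then score below 8. Section 13.6 concerns care after the study and does not place replacement therapy before the Withdrawal procedures. Section 3.4 allows review of results obtained up to withdrawal, which points to earlier data. The design also gives little reason to switch early. Rescue is permitted, and a subject unhealed at Visit 4 has already been scored when the further 4 weeks begin. This stands as a limit on size. It does not close the gap, because the 3.4 wording is discretionary and 9.2.3.1 expressly brings in the Withdrawal visit.

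**Dropping prohibited-drug users is what a PPS does, and using the last observation regardless of later treatment is a recognised strategy.** Both are true. But the plan does not say that the effect regardless of switching is what it wants, and with the PPS primary no reported result counts these subjects as failures.

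**A reader might infer that the subject leaves the FAS as well.** Exclusion criterion 10 covers "Those who need to take any prohibited concomitant medication during clinical study", and 9.1 says "The subjects who violate the inclusion/exclusion criteria will be excluded from the FAS". The documents do not support this reading. Eligibility is decided from screening and Visit 2 (8.2 note 9; 8.3.10). Sections 9.1 and 13.5 list eligibility violations separately from prohibited-drug use, and 3.4 gives a later need its own withdrawal reason. A clarifying sentence is enough.

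**A reader might infer that any acid suppressant before Week 4 should count as failure.** That could itself favour non-inferiority. Section 1.5 says PPIs take 3 days or more to improve symptoms, so early breakthrough use could be commoner on esomeprazole. With truth at the margin and 67 per arm, assumed use among otherwise relieved subjects of 5% (control) versus 2% (fexuprazan) gives 6.8% false claims, and 3% versus 1% gives 5.3%. This objection stands, and it limits the rule below.

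**Conclusion.** The gap is real and its effect is modest. As written, a failure of the assigned drug can be scored as relieved in the FAS and is absent from the primary PPS, so neither set records it. When failures switch at similar rates in both arms, the observed difference shrinks towards zero. At assumed switch rates of 5-10% of failures, the false-claim rate goes from about 3.0% to 3.2-4.3% (FAS) and from 3.1% to 3.5-3.9% (PPS). These figures rest on truth at the margin, Wald limits, the planned set sizes and equal switching among failures. The FAS figures also need the replacement to start before the final GERD-Q.

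A reader might take the 25% and 50% rows as expected error rates. The documents give no switch rate and offer nothing to support values that high, so those rows only show direction. Nor does the fix remove the effect from the primary PPS result. It corrects the FAS and makes the PPS effect visible.

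**What to change.** **In 9.2.3.1 add:** *In the FAS, a subject is counted as not relieved if, before the Week 4 assessment, the subject is withdrawn because a prohibited acid-suppressive drug is required for reflux symptoms, or if a prohibited acid-suppressive drug is taken within the 7-day recall of the GERD-Q used for the primary endpoint.* State that earlier use by a subject who stays on the assigned drug does not by itself make that subject a failure.

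**Sensitivity analyses:** the as-observed FAS result, and a PPS result that adds the subjects counted under this rule back as not relieved. The PPS definition stays as it is.

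**In 9.1 clarify** that need for such a drug arising after randomization is not an eligibility violation.

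**Cost.** The text changes are short, two results are added, and no new data are needed: 7.3.1 already records drug, dates and purpose. Relief rates fall slightly. If recall-week use is unrelated to failure, there is some power loss. Assuming one day of use spread evenly over 28 days, the share counted is use × 7/28, so 5% use gives 1.25% and 10% gives 2.5%. Multiplying 0.940 and 0.885 by one minus that share, at 67 per arm, power goes from 0.91 to 0.87 and 0.83. An open-label withdrawal decision also becomes part of the FAS endpoint, which is why the as-observed result is kept beside it.

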9.2.3.2 Secondary Efficacy Assessment

1. Proportions of subjects with symptoms relief at week 8 measured by GERD-Q Score <8

The proportions of subjects with symptoms relief by Week 8 and their 95% confidence intervals will be provided by group. The proportions of subjects with symptoms relief by Week 8 will be calculated as the cumulative symptoms relief by using the results at the time of final observation including the Withdrawal visit. To compare the control group and study group, the lower bound of the 2-sided 95% confidence intervals will be obtained by using the Chi Square test or Fisher's Exact test method. If this lower bound is greater than the non-inferiority margin of -0.1, the study group will be judged to be non-inferior to the control group. (Week 8 evaluation will only be applicable to patient receiving treatment 2)

2. Assessment on symptoms based on the diary of subjects

- CR (disappearance of heartburn, acid regurgitation, or heartburn/acid regurgitation for 7 consecutive days) is defined as the symptom score of 0 for 7 consecutive days for the first time after the first dose, and the survival time is defined as the time to reach Complete Response (CR) after the first IP administration. Kaplan-Meier plots will be drawn by treatment group, and the medians and their 2-sided 95% confidence intervals will be presented. To compare the control group and study group, the log-rank test will be used.
- The number of subjects without any heartburn, acid regurgitation, or heartburn/acid regurgitation for the first 7 days, full 4 weeks, and full 8 weeks from the first IP administration, the proportion (%) of these subjects and its 95% confidence interval will be presented by treatment group. To compare the control group and study group, the 2-sided 95% confidence intervals and p-value will be obtained by using the Chi Square test or Fisher's Exact test method.

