9.2.4.1 Adverse events

AEs will be recorded based on worsening of existing symptoms or the newly occurring treatment-emergent adverse events (TEAEs) after administration of the IP.

For TEAEs, adverse drug reactions (ADRs), and serious adverse events (SAEs), descriptive statistics (number of subjects, incidence (%), and number of cases) will be presented, and Chi-square test or Fisher's exact test will be used for analysis depending on whether cells with the expected frequency of <5 is $>20\%$ or not.

AEs, ADRs, and SAEs will be coded by system organ class (SOC) and preferred term (PT) using the medical dictionary for regulatory activities (MedDRA) version 21.0 (or higher), and coded AEs will be presented with the number of subjects, incidence, and the number of cases by treatment group. The frequency and percentage of subjects who are withdrawn due to serious adverse events or AEs will be presented and the listings will be provided.

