9.3 Criteria

Hypothesis: The study group (Fexuprazan 40 mg) is non-inferior to the control group (Esomeprazole 40 mg) in terms of the proportions of subjects with symptoms relief by Week 4.

To determine the noninferiority of the study group (Fexuprazan 40 mg) against the control group (Esomeprazole 40 mg), the **Chi Square test or Fisher's Exact test method** will be used. The lower limit of the 2-sided 95% confidence intervals for the difference between the study group and control group (study group minus control group) will be calculated, and if this lower limit is larger than the non-inferiority margin of -0.1, the study group will be declared non-inferior to the control group.

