9.4.2 Rationale for Determination of Sample Size

This study objective is to determine the non-inferiority of the study group (Fexuprazan 40 mg) compared to the control group (Esomeprazole 40 mg) in patients with erosive gastroesophageal reflux disease. The primary endpoint is the proportions of subjects with symptoms relief at week 4 measured by GERD-Q Score <8 , and the hypothesis is:

$$H_0: \pi_T - \pi_C \leq -0.1 \quad \text{vs.} \quad H_A: \pi_T - \pi_C > -0.1$$

π_T : Proportion of subjects with symptoms relief at week 4 (measured by GERD-Q score <8) in the study group (Fexuprazan 40 mg)

π_C : Proportion of subjects with symptoms relief at week 4 (measured by GERD-Q score <8) in the control group (Esomeprazole 40 mg)

The proportion of subjects with symptoms relief at week 4 of proton pump inhibitors (PPI) was considered to be 88.5%, and this value was set as the proportion of symptoms relief for the control group (Esomeprazole 40 mg). In this study, the proportion of symptoms relief of the study drug was assumed to be higher than control drug, therefore, 94.0% was set as the proportion of symptoms relief in the study group.

The number of subjects calculated by “Non-Inferiority Tests for the Difference Between Two Proportions” of PASS2020 with the non-inferiority margin of -0.1, the one-sided significance level of 2.5%, 80% statistical power, and 1:1 randomization allocation, was 53 per group. And considering a dropout rate of 20%, a total of 134 subjects will be enrolled in the study.

Non-Inferiority Tests for the Difference Between Two Proportions											
Numeric Results											
Test Statistic: Z-Test with Pooled Variance											
Hypotheses: H0: P1 - P2 ≤ D0 vs. H1: P1 - P2 > D0											
Target Power	Actual Power*	N1	N2	N	Ref. P2	P1 H0 P1.0	P1 H1 P1.1	NI Diff D0	Diff D1	Alpha	
0.80	0.80729	53	53	106	0.8850	0.7850	0.9400	-0.1000	0.0550	0.025	
* Power was computed using the normal approximation method.											

10 Data Management (Recording, Collection, Access, Protection, and Storage)

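### The non-inferiority bound is taken from a chi-square or Fisher test, so the interval that decides the primary endpoint is not specified

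*Combined protocol and SAP*

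**What the plan says.** Section 9.2.3.1 (primary endpoint, relief at Week 4) states that "the lower bound of the 2-sided 95% confidence intervals will be obtained by using Chi Square test or" Fisher's exact test, and compares the bound with -0.1. The synopsis has the same rule. Section 9.3 fixes the scale as "2-sided 95% confidence intervals for the difference between the study group and control group (study group minus control group"), again names the two tests, and uses the same margin. Section 9.2.3.2 item 1 repeats the wording for Week 8 ("the lower bound of the 2-sided 95% confidence intervals will be obtained by using the Chi Square test or" Fisher), again with -0.1, and adds that "Week 8 evaluation will only be applicable to patient receiving treatment 2".

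Section 9.4.2 sizes the trial with a different procedure: "Test Statistic: Z-Test with Pooled Variance", tested against -0.1, with the note "Power was computed using the normal approximation method".

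The only rule for choosing between chi-square and Fisher is in Section 9.2.4.1, "depending on whether cells with the expected frequency of <5 is" above 20%. It is written for treatment-emergent adverse events, adverse drug reactions and serious adverse events.

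**The concern.** The verdict needs a lower confidence limit for a difference in proportions. The chi-square and Fisher tests, as ordinarily run, return a p-value for a difference of zero. Either kind of test can be inverted at a non-zero difference to give an interval, but the plan does not say this is intended, and different inversions give different limits. Nothing else in the document names a risk-difference interval.

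The safety rule would not fill the gap if it were borrowed, because it selects a test and not an interval. It would also make the choice depend on the data.

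This is the trial's one formal hypothesis. The trial is open-label and is analysed after it ends, so the interval could be settled by someone who knows the allocation and has seen the counts. Relief rates near 90% with about 53 patients per arm are also where the common intervals disagree most visibly.

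**Working it through.** **Inputs (Section 9.4.2).** Control rate 0.885; study rate 0.940; margin -0.1; one-sided 2.5%; 53 evaluable per arm; 20% dropout; 134 in total.

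**1. The plan's own figure.** Power = Φ[(0.055 + 0.1 - 1.96 × SE_pooled) / SE_unpooled].

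- Mean rate = (0.94 + 0.885)/2 = 0.9125.
- SE_pooled = √(2 × 0.9125 × 0.0875 / 53) = 0.05489.
- SE_unpooled = √[(0.94 × 0.06 + 0.885 × 0.115)/53] = 0.05463.
- Power = Φ[(0.155 - 0.10758)/0.05463] = Φ(0.868) = 0.80729.

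At n = 52 the same formula gives 0.79984, so 53 is right. Then 53/0.80 = 66.25, rounded up to 67 per arm and 134 in total. The sizing reproduces.

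**2. What the open choice does.** For every outcome (x, y) with x, y = 0 to 53, apply the rule that the lower 95% limit exceeds -0.1, and sum the binomial probabilities. Power is taken at 0.94 vs 0.885 and one-sided error at 0.785 vs 0.885, the boundary of the null. The documents name none of these intervals; they are assumed candidates.

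| Interval | Power | One-sided error |
|---|---|---|
| Wald | 82.5% | 3.1% |
| Pooled Z (the sizing statistic used as the rule) | 82.5% | 3.0% |
| Agresti-Caffo | 79.5% | 2.5% |
| Hauck-Anderson | 78.9% | 2.1% |
| Newcombe, Farrington-Manning | 77.5% | 2.5% |
| Miettinen-Nurminen | 77.4% | 2.5% |
| Exact unconditional, score-based | 73.8% | 2.0% |
| Wald, continuity-corrected | 72.0% | 1.5% |
| Newcombe, continuity-corrected | 68.4% | 1.7% |

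An exact unconditional interval built on the unstandardised difference would be far more conservative (18.3% / 0.2%). It is left out of the range quoted in the conclusion.

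**3. How often the verdict changes (planning rates).** Wald against Miettinen-Nurminen: 5.1% of trials. Wald against continuity-corrected Wald: 10.5%. Wald against continuity-corrected Newcombe: 14.1%.

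**4. Two concrete results.**

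- 48/53 vs 47/53. The difference is 0.0189. The Wald SE is √[(0.9057 × 0.0943 + 0.8868 × 0.1132)/53] = 0.0592, so the limit is 0.0189 - 1.96 × 0.0592 = -0.097, a pass. Newcombe gives -0.105 and Miettinen-Nurminen -0.107, both fails. The score statistic against -0.1 is 1.865 (Miettinen-Nurminen) or 1.874 (Farrington-Manning), both below 1.96.
- 50/53 vs 50/53, identical observed rates. Wald gives -0.088, a pass. Newcombe gives -0.104 and Miettinen-Nurminen -0.106, both fails.

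**5. Borrowing the safety rule.** The expected number of non-responders per arm is (53 × 0.06 + 53 × 0.115)/2 = 4.64. The expected count computed from the observed margins falls below 5 in about 55% of trials, so the choice between chi-square and Fisher would be close to a coin toss.

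**6. Week 8.** If everyone without relief at Week 4 continues, Treatment 2 would hold about 53 × 0.06 = 3.2 study and 53 × 0.115 = 6.1 control patients (4.0 and 7.7 at 67 per arm). If 4/4 and 8/8 are relieved, the limit is 0.00 by Wald (pass), about -0.49 by Newcombe and -0.51 by Miettinen-Nurminen (both fail).

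**The case against.** The best defence is that the chi-square half has a natural reading. For a 2×2 table the Pearson statistic is the square of the pooled-variance Z at zero difference. Sections 9.2.3.1 and 9.4.2 together could therefore mean the difference minus 1.96 pooled standard errors, compared with -0.1. At the planning rates this rule agrees with Wald in practically every trial. The reading is coherent, but the plan does not state it, it leaves the Fisher alternative open, and its exact one-sided error at 78.5% vs 88.5% is 3.0%, above the stated 2.5%.

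Other points carry some weight:

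- The 10.5% and 14.1% figures need continuity corrections the plan never mentions. Between Wald and the score-type intervals the disagreement is about 5%, and the score-type intervals hardly differ from one another.
- Open-label conduct does not affect which interval is valid, and Section 9.1 places case adjudication before the randomization codes are disclosed. Open-label conduct matters here only because the choice of interval is still to be made.
- Section 9.4.2 labels 0.80729 a normal approximation, so it is not misreported. It is simply not the power of a score interval.
- Naming an interval does not rescue the Week 8 comparison. That subset is selected by response after randomization and is too small for a -0.1 margin. The hypothesis in Section 9.3 covers Week 4 only.

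**Conclusion.** The concern holds. The decision rule and the sample-size arithmetic are sound on their own inputs. What is wrong is the method named for the bound: it does not identify an interval for the difference, and it offers two alternatives with no rule for efficacy. Over the tabulated candidates, power at 53 per arm runs from 68.4% to 82.5% and one-sided error from 1.5% to 3.1%. Between the two most likely kinds of choice, Wald and a score interval, about 1 trial in 20 changes verdict. Even the most favourable reading of the text exceeds the stated error rate. These figures assume 53 evaluable per arm and the plan's response rates, and the candidate intervals are the review's, not the plan's.

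**What to change.** In the synopsis and Sections 9.2.3.1, 9.2.3.2 item 1 and 9.3, replace the reference to the two tests with a single interval and no data-dependent alternative. For example: two-sided 95% Miettinen-Nurminen confidence interval for π_T - π_C, with non-inferiority declared if the lower limit is above -0.10. Farrington-Manning or Newcombe would serve equally well. Make the change before any outcome data are reviewed.

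In Section 9.4.2, restate exact power for the chosen method. For Miettinen-Nurminen it is 77.4% at 53 evaluable per arm, 81.3% at 58 and 87.1% at 67.

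The cost is wording in four places and a stated power about 3 points lower at 53 per arm (80.7% to 77.4%). With 134 enrolled, 80% power holds if no more than 9 of 67 per arm are lost (13.4%). That is less than the planned 20%, and the primary set under Section 9.2.1 is the per-protocol set, which also excludes major deviators. Keeping the 20% allowance with 58 evaluable would need 58/0.80 = 72.5, so 73 per arm and 146 in total. The sponsor should say which it accepts.

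A score interval is not strictly exact. At 53 per arm the Miettinen-Nurminen error peaks at about 2.5% for control rates of 80-95% and is 2.75% at a control rate of 60%.

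For Week 8, the same interval makes the wording consistent but does not make a formal non-inferiority verdict on that subset supportable.
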